7.3 Comparator Justification

[figure not shown]
A recent systematic review and meta-analysis looking at both techniques together have shown that they both significantly decrease total opioid consumption compared to placebo.⁵ Thus this study is not looking at equivalence to placebo, it is looking for the best technique head to head.

7.4 Techniques

Technique for Anaesthetically inserted rectus sheath catheter

- 1) The procedure takes place after abdominal wall closure, prior to dressings.
- 2) From the superior aspect of the incision a point 5-7cm lateral and 3cm cranial OR at the costal margin (If this former point is superior to the costal margin) is marked for the catheter insertion.
- 3) Under U/S guidance at this marking a 16G Tuohy Needle is inserted at approximately 30-45 Degrees in either a lateral to medial direction (To avoid epigastric arteries) or caudal direction or a combination.
- 4) When the tip of the needle is just below the rectus muscle before going through the posterior rectus sheath (Intrafascular space) some of the 20mL of 0.2% Ropivacaine is infused to hydro dissect and open up the space. See figure 2 for the correct placement
- 5) The angle of insertion is then dropped to parallel with the skin and the needle is advanced further.
- 6) The 16G Epidural Catheter is then inserted through the needle to approx. 10-15cm and the needle is withdrawn slowly to ensure the catheter does not move.
- 7) The Catheter is then secured with the Securement Device.
- 8) The catheter connector, followed by the filter is then attached to the distal end of the catheter
- 9) The process is then repeated on the contralateral side.
- 10) The remainder of the 20mL of 0.2% Ropivacaine is infused on each side.

[figure not shown]
Figure 2: U/S placement location (Intrafascicular)

Technique for Surgically inserted rectus sheath catheter

- 1) The procedure takes place just prior to abdominal wall closure.
- 2) From the superior aspect of the incision a point 5cm lateral and 3cm cranial OR at the costal margin (If this former point is superior to the costal margin) is marked for the catheter insertion.
- 3) At this marking a 16G Tuohy Needle is inserted at approximately 45 Degrees in a caudal direction, parallel to the incision.
- 4) With the surgeon's other hand the inside the abdominal cavity, deep to the site of insertion, the needle is advanced until it has just passed through the rectus sheath and just lies in the pre-peritoneal plane.
- 5) The angle of insertion is then dropped to parallel with the skin and the needle is advanced further with the surgeon's other hand used to palpate the needle and ensure it remains in the correct plane.
- 6) The 16G Epidural Catheter is then inserted through the needle to approx. 10-15cm and the needle is withdrawn slowly to ensure the catheter does not move.
- 7) The Catheter is then secured with the Securement Device.
- 8) The catheter connector, followed by the filter is then attached to the distal end of the catheter
- 9) The process is then repeated on the contralateral side.
- 10) 20mL of 0.2% Ropivacaine is infused on each side.
- 11) Once the wall closure has been completed a large transparent dressing is placed over the insertion site.

Figure 3: Surgical placement location (Pre-Peritoneal)

7.5 Randomisation Procedure

Randomisation will occur via a random allocation sequence which will be made by a third party ([name]) via computer randomisation prior to the project. There will be no restrictions such as blocking on this randomisation. The concealed sequence will be in ordered closed envelopes and only once the patient is enrolled will the arm they are allocated be revealed.

7.6 Unblinding Procedure

The patient can be unblinded after all subjective testing is done on day 3 if they request.

8 Adverse Events (AE) and Serious Adverse Events (SAE)

The wellbeing and safety of participants in this research is the paramount. Although a recent systemic analysis has not linked this procedure to any adverse events (AE) or serious adverse events (SAE),⁵ possible AE and their definition will be outlined below. Unexpected AE and SAE will also be monitored for and are defined below.

The investigators are responsible for the detection and documentation of AE or SAE as defined in this protocol. During the study, there will be a safety evaluation by the investigators in Mackay every month looking at AE. Any SAE is to be reported to the principal investigator within 24 hours. This will result in a safety evaluation of all current and past cases again and a report to the head of surgery and head of anaesthetics within 5 working days. Any time there is a SAE with definite or probable causality a report will be sent to the ethics committee and the trial may be suspended or terminated early at the principle investigator's, local head of department's or ethics committee's request.

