All enrolled patient will be randomised into two even arms via random allocation sequence in numbered envelopes. A third party doctor using computer randomisation will conduct the randomisation prior to commencement of the project. The allocation will be revealed prior to closure of the abdomen where the patient will either receive a surgically placed pre-peritoneal catheter or an ultrasound guided rectus sheath catheter inserted by the anaesthetic team prior to waking up from the general anaesthetic.

These catheters will then be intermittently infused with local anaesthetic over the next 72 hours via a pump. Over this time the patients' opiate analgesic requirement and the visual analogue scale (VAS) will be monitored daily. The surgical team and the anaesthetic pain team will review the patients daily for the above and monitor for adverse effects from the procedure/local anaesthetic.

Eligibility Criteria (Inclusion and Exclusion)

Inclusion: All adult general surgical patients undergoing a midline laparotomy at Mackay base hospital

Exclusion Criteria:

- Local Anaesthetic allergy
- Catheter plastic allergy
- Multiple operations as defined as alteration of anatomy of the abdominal wall, preventing placement of catheters.
- Chronic abdominal pain as defined as abdominal pain with opiate use for > 12 weeks
- Abdomen left open
- Patient under 18 years of age
- Pregnant
- Inability of surgical/anaesthetic staff to perform procedure
- Patients with altered cognition (dementia or delirium) and therefore unable to respond to

VAS.

- Patients intubated & therefore unable to communicate

Sample Size Determination:

Calculation of the sample size was performed by using the primary endpoint of 72-hour total morphine usage post laparotomy. In a similar previous study, the total dose of administered morphine was 62mg with a standard deviation of 16mg.⁴ It was decided that a difference of 20% (12mg) would be considered clinically relevant, similar to this previous study.

Assuming $\alpha = 0.05$ and $\beta = 0.15$ (a power of 85 per cent), a total of 66 patients (33 patients per group) would be required to find there was no difference between each group¹⁰. Assuming a 10% dropout rate 72 patients need to be recruited (36 patients per group) to make this number.

2 Introduction

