In this study, the catheters will be inserted and secured by either a surgical or anaesthetic consultant. Surgical consultants and anaesthetic consultants will be orientated to the standard specified procedure (as detailed in section 7.4 of this protocol) of placement as led by [name] (Director of Surgery) prior to the commencement of this study.

3 Objectives

Null hypothesis: Surgically placed pre-peritoneal catheters are superior to ultrasound placed rectus sheath catheters at reducing post-operative pain.

The primary endpoint is:

- Total narcotic usage until day three post op. This will be measured in mg of IV Morphine. All other narcotic agents (Oral or IV) will be calculated back to IV Morphine equivalence as per dosage equivalence on MIMs.

Secondary endpoints:

- Time taken for procedure (Minutes)
- Patient blinded VAS scores at rest and coughing (0-10)
- Time till flatus (Days)
- Time till BO (Days)
- Time till discharge (Days)
- Complications
 - o Wound infection
 - o UTI
 - o VTE

4 Study Design

This will be a randomised, patient blinded trial. All enrolled patient will be randomised into 2 even arms – One to receive a surgically placed pre-peritoneal catheter, the other an ultrasound guided rectus sheath catheter inserted by the anaesthetic team prior to waking up from the general anaesthetic. Both will then receive 72 hours of intermittent Ropivacaine 0.2% boluses via these catheters.

Patients will be screened for the study when they are booked up for an emergency or elective procedure which will always or potentially require a midline laparotomy. These patients will then be consented for potential enrolment. Enrolment and allocation will be only revealed when it is sure that the patient does not meet any of the exclusion criteria in theatre prior to closure of the abdomen via randomised numbered envelopes.

These numbered envelopes will be generated prior to the start of the study by a 3rd party doctor. This doctor, who is not involved in the study in any other way, will use a random allocation sequence generated by computer using non-blocking randomisation.

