Over the first 72hours the patients' opiate analgesic requirement, the visual analogue scale (VAS) and potential complications will be monitored daily by the surgical team and recorded on the data collection tool. During this time the anaesthetic team will also review the patient to monitor the local anaesthetic boluses are being administered correctly via the pumps and to look for adverse effects from the

procedure/local anaesthetic as well. After the 72 hours, unless to patient has ongoing pain issues, the surgical team alone will continue to see the patient daily and record any delayed complications until discharge.

This follow up, other than recording on the data collection sheet, is currently routine care for patients post laparotomy with rectus sheath catheters and will not significantly increase workload for the teams involved during the trial period.

5 Study Population

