6.2.2 Day 1,2,3

Data collection will begin with documenting intraoperative analgesia & anaesthesia requirements. Subsequently data will be collected on the premise of the VAS 12 hours post-operatively (at rest & at coughing) by the Surgical/Anaesthetic Registrar or Consultant. On the surgical ward round the registrar or consultant will ask whether the patient has opened bowel or passed flatus. All data will be recorded on the data collection tool, which will be placed in the patient's chart. The morphine equivalent analgesia can be, but does not have to be filled in. This can be retrospectively analysed for the patient med chart, chart notes, and anaesthetic pain round by the investigators. The investigators will be directly involved in reviewing each patient recruited in this study.

At any stage any complications can be written at the bottom of the Data collection tool.

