8.2 Time Period, Frequency, and Method of Detecting AEs and SAEs

All adverse events will be monitored for and recorded daily between recruitment and discharge from hospital (Usually 5+ days). Late adverse events will be assessed on follow up post laparotomy (Usually at approximately 4 weeks). This will be recorded on either the data collection tool or their electronic notes up to 2 months post procedure.

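### Patients may learn their arm from day 3, before discharge and sometimes before first flatus and bowel opening, in a trial whose only blind is the patient's

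*Protocol*

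**What the plan says.** The design section (section 4) describes the blinding in one line: "This will be a randomised, patient blinded trial". The title calls the trial single blinded. No section blinds the consultants who place the catheters or the surgical and anaesthetic teams who follow the patient.

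Section 7.6 is the whole unblinding rule: "The patient can be unblinded after all subjective testing is done on day 3 if they request". It does not mention hour 72, first flatus, first bowel opening or discharge, and it does not ask for the date of unblinding to be recorded. No other section delays unblinding further.

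The outcomes that bear on this are:

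- **Opioid use (primary).** Section 3 defines it as "Total narcotic usage until day three post op". The synopsis treats it as a 72-hour total: "Calculation of the sample size was performed by using the primary endpoint of 72-hour total morphine usage post laparotomy". Section 4 has the same window: "Over the first 72hours the patients' opiate analgesic requirement, the visual analogue scale (VAS) and potential complications will be monitored daily by the surgical team".
- **Flatus and bowel opening (secondary).** Both are times in days with no upper limit (section 3). Section 6.2.2, on days 1 to 3, says how they are learned: "On the surgical ward round the registrar or consultant will ask whether the patient has opened bowel or passed flatus".
- **Discharge (secondary).** Also a time in days. Section 8.2 indicates how late it usually falls: "All adverse events will be monitored for and recorded daily between recruitment and discharge from hospital (Usually 5+ days".

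**The concern.** The rule ends the blind when the day-3 subjective assessments end. That fully protects the pain scores. Discharge usually comes later, and flatus and bowel opening come later in some patients. A patient who knows the arm may report bowel function differently, press for or resist discharge, or ask for more or less opioid in whatever remains of the 72 hours.

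Two features make this worth correcting. The patient's blind is the only one in the trial, so nothing else protects these outcomes once it is lifted. Unblinding is also on request, so the unblinded patients select themselves. Because no date is recorded, the analysis could not later separate outcomes that arose before unblinding from those that arose after it.

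**Working it through.** **Step 1. When each outcome is complete, against the section 7.6 trigger**

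| Outcome | Complete, per the protocol | Closed when unblinding is first allowed? |
|---|---|---|
| Pain scores, rest and cough | Day-3 assessment | Yes |
| Opioid total | 72 hours | Depends on the hour of day-3 testing |
| First flatus, first bowel opening | When they occur; no limit | Only in patients who have reached them |
| Discharge | Usually five days or more | Usually not |

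**Step 2. Discharge.** With discharge at day 5, 5 − 3 = 2 days follow the permitted unblinding, which is 2/5 = 40% of a five-day interval. Longer stays have more. This uses only the protocol's own figure.

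**Step 3. Flatus and bowel opening.** Only patients without the event by day 3 are affected. The protocol gives no figure for how many, so no size can be attached.

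**Step 4. Opioid total, hours exposed.** If day-3 testing falls t hours after surgery, the exposed time is h = max(0, 72 − t). The protocol does not give t. Assuming an 08:00 ward round on day 3:

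- surgery ending 02:00: t = 78, h = 0
- surgery ending 12:00: t = 68, h = 4
- surgery ending 20:00: t = 60, h = 12

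The one stated time for a pain score is 12 hours after surgery (section 6.2.2). If it were repeated every 24 hours, which the protocol does not say, the third would fall at 60 hours and again leave h = 12. The working range is therefore 0 to about 12 hours, or 0 to 12/72 = 17% of the window. A later finish or an earlier round would lengthen it hour for hour.

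**Step 5. Opioid total, size of a possible shift.** Inputs from the sample-size sections: mean 62 mg, SD 16 mg, target difference 12 mg. The synopsis gives 33 evaluable patients per group for 85% power. Taking alpha 0.05 as two-sided, 33 per group gives 85.1% by the noncentral t and 86.1% by the normal approximation, so the synopsis figure is reproduced. Section 10.2 gives 31 per group instead; that is a separate matter.

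Assumptions: opioid use is even over 72 hours (62/72 = 0.86 mg per hour); half of one arm and nobody in the other asks (f = 0.5); those patients change later use by 20% (c = 0.20). The amount exposed is R = 62 × h/72, and the shift in the arm mean is b = R × f × c.

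| h | R (mg) | b (mg) | b/12 | Power if b works against the effect (33 per group, normal approximation) |
|---|---|---|---|---|
| 0 | 0 | 0 | 0% | 86.1% |
| 4 | 3.44 | 0.34 | 2.8% | 84.1% |
| 8 | 6.89 | 0.69 | 5.8% | 81.9% |
| 12 | 10.33 | 1.03 | 8.6% | 79.5% |

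A shift in the other direction would raise the chance of a positive result instead (88.0%, 89.6% and 91.1% for h = 4, 8 and 12). If every patient in one arm asked and nobody in the other, b would be 0.69 mg at h = 4 and 2.07 mg at h = 12. If both arms asked equally and reacted alike, b would be zero.

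**The case against.** Several counter-arguments have force.

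**The primary endpoint may not be exposed at all.** A reader might infer that the day-3 assessment comes before hour 72, so that the primary endpoint is routinely collected open-label. The documents do not support that. On their face the opioid endpoint and the unblinding rule both end on day 3. No hour is set for the testing, and emergency laparotomies, which are included, can finish at any time of day. Where overlap exists, the illustrated shift is small, and asking in one arm only is a pessimistic assumption. This stands.

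**Evidence for bowel questioning after day 3 is thin.** A reader might take the chart-review row of the schedule as proof that flatus and bowel data are newly collected after day 3. That row also marks opioid use, whose window has closed by then and which section 6.2.2 allows to be filled in retrospectively. The ward-round question belongs to days 1 to 3, and after 72 hours section 4 mentions recording only delayed complications. What remains is that the endpoints have no day-3 limit, so a late event still counts.

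**Discharge gains little from a patient blind.** The surgical team that sees the patient daily until discharge is not blinded, so this endpoint is open on the staff side throughout. That stands, and it limits what any change to section 7.6 can achieve.

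**There is no placebo to discover.** Both arms have catheters and the same ropivacaine regimen, so knowing the arm may alter behaviour little. This is plausible. The protocol offers no evidence either way.

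**Section 7.6 is open about when the blind ends.** A reader might call it a contradiction of the patient-blinded description. It is not: the endpoint lists attach the patient blind by name only to the pain scores, which the rule protects. The point concerns a poorly chosen time, not inconsistent text.

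**Conclusion.** The point holds for the secondary endpoints. On the protocol's own figure, discharge usually falls at least about 2 days after patients may learn their arm. First flatus and bowel opening are exposed only in patients who have not reached them by day 3, an unknown number. For the opioid total the exposure is 0 to about 12 hours under assumed clock times. The illustrative shift is at most about 1.0 mg, against a 12 mg target, if half of one arm asked and changed use by 20%. The result depends on how many patients ask, which the documents do not say. Severity is minor and confidence moderate: the sequence of events is clear for discharge, but the size of any bias is not known.

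**What to change.** Replace the sentence in section 7.6 with, for example: *A patient who asks may be told the allocation after discharge from the index admission, once the 72-hour opioid total, first flatus, first bowel opening and discharge date have been recorded. The date of, and reason for, any earlier unblinding will be documented.*

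The cost is one protocol sentence, through the amendment route in section 15.6, and a few days' wait for patients who ask. Sample size, treatment and assessments do not change. The amendment removes only patient-side bias; outcomes that depend on staff decisions, discharge above all, remain unblinded on the staff side.

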8.1 Definition of an Adverse Event (AE) and a Serious Adverse Event (SAE)

Regarding the insertion/Catheter site:

- A simple abdominal wall haematoma (Bruise) will be recorded as AE. If it is associated with a Haemoglobin drop of >30 or requires a blood transfusion it will be recorded as a SAE and notified as above.
- Any damage to one of the intra-abdominal organs on insertion of the needle will be recorded as a SAE.
- A wound infection is defined by the treating team. This is because there is no standard laboratory test for defiantly deciding if a wound is infected or not, except clinically. This complication is common post laparotomy and will be monitored for up to 2 months post the procedure. If there is signs of wound infection prior to 72 hours the catheters must be withdrawn early and the reasons why clearly documented. If the infection results in a return to theatre or sepsis (As defined by SIRS) criteria or results in death it will be recorded as a SAE, otherwise it will be recorded as an AE.

Regarding the local anaesthetic, a large number of adverse events have been reported during clinical development, the majority related to the expected effects of the block and to the clinical situation rather than reactions to the drug, but are to be reported as follows:

- Nausea - AE
- Temporary paraesthesia - AE
- Headache - AE
- Urinary retention – AE, Unless it results in a UTI (Defined as >200 Leukocytes +/- bacteria in urine MCS and either symptoms of a UTI or sepsis with no other source identified). If this results in sepsis (As per SIRS Criteria) this will be recorded as an SAE, otherwise a simple UTI will be recorded as an AE
- Rare systemic toxicity from the local anaesthetic - The signs/symptoms the treating doctors and investigators will look out for are dysarthria, muscular rigidity, muscle twitching, unconsciousness, convulsions, hypoxia, hypotension, bradycardia, arrhythmias and cardiac arrest. If any of these are found with no other obvious cause, the local anaesthetic infusion is to be withheld. If the signs/symptoms resolve after the infusion is stopped, it is likely a causal relationship and any will be classified as a SAE and need to be immediately (Within 24hrs) reported to the principal investigator. Specialised local anaesthetic blood level tests may be ordered to help assess causality.

Other than the specific ones as stated above, this study defines any other complication a SAE when there is likely causal relationship between the procedure and/or local anaesthetic infusion and that complication such that it:

- Results in death
- Is life threatening
- Requires hospitalisation or prolongation of an existing hospitalisation.
- Results in disability/incapacity

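### Wound infection, a named secondary endpoint, has no case criteria and rests on the opinion of an unblinded treating team, so it is not reproducible and differential ascertainment between arms cannot be excluded

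*Protocol*

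**What the plan says.** The Synopsis and section 3 list "Wound infection" first among the complications that form a secondary endpoint, beside UTI and VTE.

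Section 8.1 sets the case rule: "A wound infection is defined by the treating team. This is because there is no standard laboratory test". The reason in full is that there is "no standard laboratory test for defiantly deciding if a wound is infected or not, except clinically". The section then separates serious from non-serious infections by return to theatre, sepsis on SIRS criteria, or death.

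For UTI, section 8.1 does give a case definition: "Defined as >200 Leukocytes +/- bacteria in urine MCS and either symptoms of a UTI or sepsis with no other source identified".

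On who inserts, section 2 says "the catheters will be inserted and secured by either a surgical or anaesthetic consultant", and the Synopsis that "the patient will either receive a surgically placed pre-peritoneal catheter or an ultrasound guided rectus sheath catheter inserted by the anaesthetic team". On who records, section 4 has the surgical team monitor complications daily for 72 hours, with the anaesthetic team also reviewing for adverse effects. After that, unless pain issues persist, "the surgical team alone will continue to see the patient daily and record any delayed complications until discharge". Section 4 describes the trial as patient blinded, and allocation is opened in theatre. Late complications are taken from a chart review at 2 months (section 6.2, Chart Follow up).

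**The concern.** A comparative endpoint needs a rule that two assessors could apply to the same wound and reach the same answer. Section 8.1 supplies an opinion instead. A borderline wound may be counted by one doctor and not by the next, and the result cannot be compared with other trials.

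The assessors also know the allocation. The team that records complications belongs to the specialty that placed the catheter in the pre-peritoneal arm, while another department placed it in the ultrasound arm. Without criteria, nothing limits the effect of that knowledge on a doubtful call. The trial asks whether the surgeons' technique is the better one, and section 14 expects the results to change local policy, so the complication comparison will be read as safety evidence.

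**Working it through.** The protocol states no infection rate and no figure for this endpoint, so there is no figure to reproduce. The check is a comparison of sections, followed by an illustration on assumed inputs.

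**Step 1: is there a case definition elsewhere?** No. The criteria in section 8.1 (return to theatre, SIRS sepsis, death) grade an infection that has already been called. Section 6.3.1 only lists the event. Section 8.3 has investigators review documentation of an event but gives no rule for what counts.

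**Step 2: does the stated reason support the rule?** No. It shows that the diagnosis is clinical, not that clinical criteria cannot be written. The UTI definition in the same section combines a urine finding with symptoms or sepsis.

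**Step 3: which wound and which window?** The bullet stands under the insertion/catheter-site heading but calls the complication common after laparotomy. Section 9.2 names catheter and wound together. The counted site is therefore open. Section 8.1 monitors for up to 2 months, whereas section 11 makes 2 months the minimum before the data set is complete.

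**Step 4: what is the same in both arms and what differs?**
- Same: the rule, the daily review, the follow-up, the chart review, and general surgeons performing the laparotomy.
- Different: the specialty that inserts the catheter.
- Not provided in either arm: a blinded or independent assessment of infection. The independent registrar in section 11 audits the spreadsheet, and the monitors in section 12 are three surgical co-authors.

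**Step 5: illustration.** Input from section 5.1: 36 patients per arm. Assumptions: all 36 assessed, the same true rate p in both arms, and labelling proportions s1 and s2.

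Recorded infections = 36 × p × s. Apparent risk ratio = s2 / s1, which does not depend on p.

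At p = 0.20:

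| s1 | s2 | Recorded, arm 1 | Recorded, arm 2 | Ratio s2/s1 | Ratio if roles reversed |
|---|---|---|---|---|---|
| 0.9 | 0.9 | 6.5 | 6.5 | 1.00 | 1.00 |
| 0.9 | 0.8 | 6.5 | 5.8 | 0.89 | 1.13 |
| 0.9 | 0.7 | 6.5 | 5.0 | 0.78 | 1.29 |
| 0.9 | 0.5 | 6.5 | 3.6 | 0.56 | 1.80 |

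For example, 36 × 0.20 × 0.9 = 6.48, 36 × 0.20 × 0.7 = 5.04, and 0.7 / 0.9 = 0.78.

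Across other assumed rates, 90% against 70% or 50% gives 3.2 against 2.5 or 1.8 at p = 0.10, and 8.1 against 6.3 or 4.5 at p = 0.25.

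**Step 6: would this produce a false significant result?** Take power ≈ Φ[(|p1 − p2| − 1.96 × SE0) / SE1], with SE0 pooled and SE1 unpooled, two-sided 0.05 assumed. At p = 0.25 with labelling 0.9 and 0.5, p1 = 0.225, p2 = 0.125, SE0 = 0.0896 and SE1 = 0.0888. Then (0.100 − 0.1756) / 0.0888 = −0.85, and Φ(−0.85) = 0.20. At p = 0.10 with 0.9 and 0.7 the result is 0.05. The chance of p < 0.05 over these settings is about 5% to 20%. Any distortion would usually appear as a misleading estimate and not as a significant finding. With counts this small the normal approximation is rough.

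**The case against.** The rule, the team, the visits and the window are identical in both arms. General surgeons open and close the abdomen in both, so their stake in the laparotomy wound does not depend on allocation; only the catheter step differs. A consultant inserts the catheter, whereas a registrar or consultant records findings on the ward round, so the person making the call need not be the inserter. Anaesthetists also review patients for 72 hours, section 8 adds a monthly safety evaluation, and section 8.3 has investigators review notes, laboratory results and imaging for each event. Wound infection is one part of an unpowered secondary list.

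Most of this stands, and it sets the limits of the point. That the treating team is the surgical team is itself an inference from section 4. None of it supplies a definition or a blinded assessor, however, and section 8.1 fixes the rule itself and does not leave it open.

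Three stronger readings are tempting and are not supported:
- **That infections are in fact counted differently in the two arms.** The documents show an opportunity, not an effect. Over-calling, under-calling and no difference in the surgical arm all fit the text.
- **That the same opinion decides AE or SAE status.** Section 8.1 gives explicit criteria for that split once an infection has been called.
- **That a chart definition would protect the opioid primary endpoint.** Section 8.1 ties early catheter removal to signs of infection in real time. A definition applied at 2 months does not alter that.

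**Conclusion.** The point holds as a defect of definition combined with unblinded assessment. Wound infection as specified is not reproducible, the counted site is ambiguous, and differential ascertainment is possible with size and direction unknown. The ratios of 0.56 to 0.89, or 1.13 to 1.80 in reverse, rest wholly on assumed rates and labelling proportions and are not estimates for this trial. Equal imperfect labelling would leave the ratio at 1.0. Because the endpoint is secondary with few expected events and the remedy is inexpensive, this is a cheap improvement and not a threat to the trial's main conclusion.

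**What to change.** For the endpoint only, replace the treating-team rule in section 8.1 with one published clinical surgical-site-infection definition and a fixed time window that fits the 2-month follow-up. State whether laparotomy-wound and catheter-site infections are counted separately. Apply the definition to every patient, not only those already labelled infected, at the 2-month chart review in section 6.2. This must precede the de-identification and disposal in section 11, after which cases could not readily be re-examined.

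Withhold the catheter-procedure page from the existing reviewer where feasible. Masking will be incomplete, since other notes may reveal the arm and section 6.2.2 has the investigators reviewing every patient in person. If the section 11 registrar were asked to adjudicate, that would be a new role.

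The treating team's diagnosis continues to guide care and AE recording, so clinical management does not change.

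Cost: a wording change, a few fields on the chart-review form, and some review time for 72 charts. Limitation: unblinded staff write the notes on which the review depends, so missed infections need not be equal across arms. The change reduces possible bias but does not remove it.
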